5.6.3.1 CNS Symptoms Temporally Associated with ARIA-E MRI Findings

CNS symptoms temporally associated with ARIA-E are defined as onset or worsening of CNS symptom(s) that is/are temporally associated with ARIA-E MRI findings. CNS symptoms experienced by the participant that are new or worsened since the last MRI without ARIA-E are collected in a CNS Symptoms Request Form before the MRI takes place at a visit. To identify CNS symptoms temporally associated with ARIA-E MRI findings, the following definitions will be used:

NEW CNS symptoms: If there is any AE reported in the eCRF with “Reported on the MRI CNS symptoms request form” = Y that is [new since date of most recent MRI scan showing no ARIA-E findings] AND is [ongoing or ends between the date of most recent site visit prior to date of MRI scan showing new ARIA-E (MRI) and date of MRI scan showing ARIA-E resolution (MRI)] then ARIA-E should be classified as associated with CNS symptoms

OR

WORSENED CNS symptoms: If there is any AE reported in the eCRF with “Reported on the MRI CNS symptom request form” = Y that is [started before the date of most recent MRI scan showing no ARIA-E findings] AND is [ongoing or ends between the date of most recent site visit prior to date of MRI scan showing new ARIA-E (MRI) and date of MRI scan showing ARIA-E resolution from MRI data] AND [there is an increase in severity grading] then ARIA-E should be classified as associated with CNS symptoms.

The CNS symptoms temporally associated with ARIA-E MRI findings will be listed and summarized by treatment group and within this also by APOE $\epsilon 4$ genotype (by number of alleles).

5.6.4 Laboratory Data

Laboratory data will be summarized for each assessment visit using descriptive statistics of absolute values and change from baseline values. In addition, the frequency of participants with abnormal laboratory values will be summarized.

5.6.5 Vital Signs

Vital signs assessments include systolic blood pressure, diastolic blood pressure, and pulse rate measured throughout the study. Vital sign measurements will be summarized for each assessment visit using descriptive statistics of absolute values and change from baseline values. In addition, the frequency of participants with abnormal results will be summarized.

5.6.6 ECGs

ECG data will be summarized for each assessment visit using descriptive statistics of absolute values and change from baseline values for the following parameters:

- Heart rate
- QRS duration
- RR interval
- PR interval
- QT interval
- QT corrected using Bazett's formula (QTcB) and QT corrected using Fridericia's formula (QTcF)

In addition, ECG overall interpretations will be summarized by visit.

5.6.7 Columbia-Suicide Severity Rating Scale (C-SSRS)

The [C-SSRS](#) is an assessment tool used to assess the lifetime suicidality of a participant (C-SSRS at baseline) as well as any new instances of suicidality (C-SSRS since last visit). The structured interview prompts recollection of suicidal ideation, including the intensity of the ideation, behavior, and attempts with actual or potential lethality.

The highest post-baseline suicidal ideation, suicidal behavior, and self-injurious behavior without suicidal intent will be summarized. In addition, change from baseline to worst post-baseline assessment in suicidality categories will be summarized.

5.6.8 Safety of Home Administration by the Study Partner

Descriptive analyses will be performed to assess the safety of home administrations of study drug by the study partner. These will compare data at a participant level and at an injection level.

Participant Level

On the participant level, a descriptive table will show:

- Number and frequency of participants with at least one home administration by study partner
- Number and frequency of participants who changed the study partner during the study (overall)
- Number and frequency of participants with different overall number of changes in study partner
- Total number of home administrations by study partner per participant (descriptive statistics)
- Percentage of possible home administrations by study partner (i.e., number of actual home administrations by study partner divided by maximum possible number) per participant (descriptive statistics)
- Percentage of participants who received home administration by study partner at each visit (starting from Week 26, excluding planned in-clinic visits; line plot)
- First week with home administration by study partner
- Heat map of administrations by study partner or HCP at home or at site

The summaries above will be presented for the SE, OH-SE, and/or the H-SE analysis set as appropriate.

Furthermore, participants will be grouped in the following way:

- Participants who have had no home administrations by their study partner
- Participants who have been dosed at home by their study partner at least once

The threshold of 1 home administration by study partner may be varied for additional exploratory, data-driven analyses.

For these two groups, demographic data and baseline characteristics will be summarized as described in Section 5.7.2. Furthermore, demographics and characteristics of all study partners will be summarized.

An AE overview table will summarize the AE profile by group. Selected AE tables of ISRs, systemic injection reactions, and hypersensitivity will provide the frequency of these events by group. Additionally, medication errors will also be summarized descriptively by group.

Injection Level

On the injection level, each single injection of study drug from Week 26 onwards (after the scheduled training of study partners at the site) will be grouped in the following way:

- Home administration by study partner

Gantenerumab—F. Hoffmann-La Roche Ltd

Statistical Analysis Plan: WN29722 (GRADUATION)

- Home administration by Health Care Professional (HCP)
- In clinic administration by study partner
- In clinic administration by HCP

The frequency of medication errors, ISRs, systemic injection reactions, and hypersensitivity will be summarized descriptively for home administrations by study partner vs. the combined group of all other administrations. The denominator in the calculations of percentages is here the number of administrations in each group (not the number of participants).

Other comparisons between home administrations by the study partner and other groups may be added.

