5.1 GENERAL CONSIDERATION

In the following sections, for all continuous variables for which descriptive statistics are indicated, the following statistics will be reported: the number of observations, the mean, median, standard deviation, and minimum and maximum. The 25th and 75th percentiles (Q1 and Q3) will also be reported for selected tables. Descriptive summaries of discrete data will include frequencies expressed in terms of number and percentage of participants.

For safety endpoints, the baseline is defined as the last available assessment prior to first study drug intake. For all other assessments, the baseline is defined as the last available assessment before or on the day of first study drug intake, unless specified otherwise.

All PD analyses and all clinical efficacy analyses will be performed on the ITT analysis set, unless specified otherwise. Safety analyses will be performed on the SE analysis set, except for analyses of MRI findings which will be performed on the M-SE analysis set and analyses of home administrations by study partner that will be performed on the SE, OH-SE, or H-SE analysis sets, as appropriate.

All analyses will be purely descriptive or exploratory without any formal hypothesis testing. For exploratory tests, a two-sided significance level of 5% will be used.

In general, missing outcome data will not be replaced or imputed unless specified otherwise. Number and percentage of missing data points will be reported for each visit for key endpoints of interest.

In statistical models using change from baseline of a given outcome measure as the dependent variable, participants with missing baseline outcome measure will be

Gantenerumab—F. Hoffmann-La Roche Ltd

Statistical Analysis Plan: WN29722 (GRADUATION)

18

Clinical Study Report: gantenerumab - F. Hoffmann-La Roche Ltd

Protocol Number: WN29722

Report Number: 1117435

18

excluded from the analysis. There will be no imputation of baseline value for outcome measures.

The impact of the COVID-19 pandemic on the study and its conduct will be monitored and the overall impact will be assessed and described in the Clinical Study Report.

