5.6 SAFETY ANALYSES

Descriptive statistics will be used to analyze all safety data collected in SE analysis set, unless otherwise specified. Safety data collected during the safety follow-up will also be included but may be summarized in separate tables. Safety analyses will be assessed through summaries of exposure to study treatment, adverse events, changes in laboratory test results, MRI findings, changes in vital signs and ECGs, changes in C-SSRS scores and immunogenicity.

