5.6.2 Adverse Events

All verbatim Adverse Events (AE) terms will be coded using the Medical Dictionary for Regulatory Activities (MedDRA) version that is current at the time of the analysis (Version 24.1 or higher), and AE intensity will be graded according to the scale defined in Table 2 in Section 5.3.3 of the study protocol (mild/moderate/severe). The frequency of each AE preferred term will be defined as the number of participants experiencing at least one occurrence of the event. Each table will present the overall number and percentage of participants experiencing at least one AE and the total number of AEs reported. Percentages will be based on the number of participants in the SE analysis set. In summary tables, AEs will be sorted by body system (also referred to as System Organ Class, in decreasing order of overall incidence), then by preferred term (in decreasing order of overall incidence). The summary tables will be restricted to treatment-emergent AEs, i.e., AEs that occur on or after the day of first study drug, and to those AEs with onset no later than 17 weeks after last dose of study drug.

Non-treatment-emergent AEs (with onset before the first dose) will be listed, and AEs occurring more than 17 weeks after the last dose will be summarized.

The following safety information will be summarized for treatment-emergent AEs:

- AEs, AEs by greatest intensity, AEs related to study drug, AEs related to radioligand
- SAEs, SAEs by greatest intensity, SAEs related to study drug
- AEs leading to discontinuation of study drug
- AEs leading to dose modification (dose interruption, dose reduction, or delayed up-titration). Delayed up-titration at any given visit is defined as the simultaneous occurrence of the following two tickboxes in the eCRF Adverse Events form:
 - Action taken with Gantenerumab due to AE/SAE: Dose Not Changed
 - Was dose regimen modified from protocol schedule? Yes
- AEs resulting in death
- Injection site reaction (ISR) signs and symptoms
- Systemic injection reactions (AEs with eCRF tickbox “systemic injection reaction” selected)
- Hypersensitivity AEs
- AEs associated with medication errors, AEs of medication errors

The impact of the COVID-19 pandemic on the safety data will be assessed by reviewing the following:

- Confirmed or suspected COVID-19 AEs
- AEs associated with COVID-19
- Potential long COVID-19 symptoms

The following data handling rules will be applied for all AE summary tables:

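### SAP 5.6.8 fixes no analysis set for its home versus no-home AE tables; on SE, everyone who stops before Week 26 counts as no-home, which distorts stop-related rows

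*SAP*

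**What the plan says.** SAP 5.6.8 forms two groups: participants never dosed at home by their study partner, and "Participants who have been dosed at home by their study partner at least once". By group it plans an AE overview ("An AE overview table will summarize the AE profile by group"), tables of ISRs, systemic injection reactions and hypersensitivity, and a summary of medication errors.

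On the analysis set:

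- Inside 5.6.8, the only set sentence comes before the AE tables and looks backward to the uptake items: "The summaries above will be presented for the SE, OH-SE, and/or the H-SE analysis set as appropriate".
- SAP 5.1 leaves three sets open: "analyses of home administrations by study partner that will be performed on the SE, OH-SE, or H-SE analysis sets, as appropriate".
- The defaults lean to SE. SAP 5.6 says "Descriptive statistics will be used to analyze all safety data collected in SE analysis set, unless otherwise specified", and SAP 5.6.2 says "Percentages will be based on the number of participants in the SE analysis set". SAP 5.4 also fixes SE for tables that include amyloid change by this same grouping.
- SAP 4 defines OH-SE as SE without those who discontinued study drug before Week 26, and H-SE as those with at least one partner home dose.

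On timing, SAP 5.6.2 counts AEs from the day of first dose to 17 weeks after the last dose. Protocol 4.3.2.1 keeps the first seven doses (Day 1 to Week 24) in the clinic. The injection-level part of 5.6.8 does start later, with "each single injection of study drug from Week 26 onwards (after the scheduled training of study partners at the site").

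**The concern.** H-SE has no no-home column, so the real choice is SE or OH-SE, and the SAP does not make it. On SE, group membership depends on staying on drug: nobody can join the home group without reaching Week 26, and anyone who stops sooner is no-home by construction. The two columns can then differ when home dosing does nothing.

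Evaluating the feasibility of home dosing is a stated purpose of the study (Protocol 3.1.1). SAP 5.8.1 puts the 5.6.8 analyses in the interim report that is meant to support a possible filing. Nothing is tested (SAP 2), so readers will compare the columns by eye. The injection-level tables offer a cleaner view for four of the five outputs: "The frequency of medication errors, ISRs, systemic injection reactions, and hypersensitivity will be summarized descriptively for home administrations by study partner" against all other administrations. The AE overview has no such counterpart.

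**Working it through.** **Dose count.** The schedule gives 3 + 3 + 6 + 68 (Weeks 36 to 103) = 80 administrations, which matches Protocol 4.6.3. Seven of them fall before Week 26. That period is 26/104 = 25% of a completer's follow-up to Week 104, and 26/52 = 50% of the first 52 weeks. The documents give no figure for the comparison itself.

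**Null model.** Home dosing has no effect and every first home dose is at Week 26. Inputs:

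- N = 192 enrolled (SAP 3).
- Drop-out D by Week 104: 15%, 25% or 35%, at a constant rate. SAP 3 names around 35% for several uncertainties together; the rest is assumed.
- Uptake u among those reaching Week 26: 50%, 70% or 90% (assumed).
- AE-led share s of stops: 20% or 40% (assumed).

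**Formulas.**

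- Stop before Week 26: e = 1 − (1 − D)^(26/104)
- Home fraction: h = u(1 − e)
- Home group, stopped by Week T: q = 1 − (1 − D)^((T − 26)/104)
- No-home group on SE, stopped by Week T: p = [e + (1 − u)(1 − e)q] / (1 − h)
- AE-led stops: s·q (home) and s·p (no-home)

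**Middle case (D = 25%, u = 70%).** e = 0.0694, about 13 people. h = 0.7 × 0.9306 = 0.6514, so about 125 home and 67 no-home.

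- Week 104: q = 0.1941; p = (0.0694 + 0.3 × 0.9306 × 0.1941)/0.3486 = 0.3545
- Week 52: q = 0.0694; p = (0.0694 + 0.3 × 0.9306 × 0.0694)/0.3486 = 0.2547

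| AE-led stops, s = 40% | No-home | Home | Gap | Standard error |
|---|---|---|---|---|
| SE, Week 104 | 14.2% | 7.8% | 6.4 | 4.9 |
| SE, Week 52 | 10.2% | 2.8% | 7.4 | 4.0 |
| OH-SE, Week 104 | 7.8% | 7.8% | 0 | |
| OH-SE, Week 52 | 2.8% | 2.8% | 0 | |

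**Range on SE.** The smallest gap is at D = 15%, u = 50%, s = 20%; the largest is at D = 35%, u = 90%, s = 40%. No-home is always higher.

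- Week 104: 0.2 × (18.25 − 11.48) = 1.4 points to 0.4 × (66.1 − 27.6) = 15.4 points
- Week 52: 0.2 × (11.3 − 4.0) = 1.5 points to 0.4 × (58.0 − 10.2) = 19.1 points

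**Any-AE row on SE.** Assume a constant AE hazard giving 80% of completers an AE by Week 104, counted to 17 weeks after the last dose.

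- Drawn independently of stopping, the middle case gives 77.9% home versus 69.6% no-home at Week 104 (gap 8.3, standard error 6.7), and 55.2% versus 51.5% at Week 52 (gap 3.7, standard error 7.6).
- That treatment is inconsistent with AE-led stops, because a person who stops for an AE has had one. With the link added by simulation, the Week 104 gap is about 6 points (s = 20%) or 4 points (s = 40%), home higher. At Week 52 it is about +1 or −1. Across the grid, with 70% to 90% of completers having an AE, Week 52 runs from about −5 to +6.

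**Event start.** Take D = 35%, u = 70%, and an event with 40% risk by Week 104 that does not drive stopping:

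| Set and event start | No-home | Home |
|---|---|---|
| SE, first dose | 33.7% | 41.3% |
| SE, Week 26 | 24.8% | 33.3% |
| OH-SE, first dose | 41.3% | 41.3% |
| OH-SE, Week 26 | 33.3% | 33.3% |

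The analysis set drives the gap. The start date does not.

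**Late starters on OH-SE.** With first home doses spread evenly over Weeks 26 to 36, middle case, s = 40%, AE-led stops are 8.8% no-home versus 7.3% home at Week 104, and 3.9% versus 2.3% at Week 52. Over the grid at s = 40%, 0.6 to 5.1 points remain at Week 104 and 0.6 to 6.4 at Week 52.

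**The case against.** The strongest reply is that the SAP foresaw the problem. It created a set for participants who had the opportunity for home dosing and allows it for these analyses, so a sensible team may well choose it. The harm depends on SE being chosen, and no sentence mandates SE for these tables. That is right, but a prespecified plan should not leave open a choice in which one option is distorted by construction and is also where the defaults lean.

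Other points stand and limit the finding:

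- SAP 5.6.8 does not list the overview's rows, and SAP 1 leaves output layouts to other documents. AEs leading to discontinuation appear among the overall summaries in SAP 5.6.2; whether the by-group overview shows them is not stated.
- A reader might infer that on SE the home group must show more participants with any AE. Once AE-led stops count as AEs, that direction is not assured, and at Week 52 it can reverse.
- A reader might infer that the first-dose start biases the comparison. On OH-SE it creates no gap in the null model, and counting treatment-emergent AEs from first dose is conventional.
- All the tables are descriptive, four of the five outputs have Week 26 injection-level counterparts, and SAP 5.7.1 reports withdrawals by reason and visit.

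**Conclusion.** The concern holds, at modest size. The set is unfixed. If SE is used, stop-related results look worse without home dosing even under no effect: 6.4 points at Week 104 and 7.4 at Week 52 in the middle case, or 1.3 and 1.9 standard errors (6.4/4.9 and 7.4/4.0). This rests on assumed drop-out, uptake and AE-led share, on some participants stopping before Week 26, and on the overview carrying such a row. The any-AE row is distorted by unequal exposure, but in the middle case the gap is within about one standard error and has no fixed sign, so no directional claim should be made for it.

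The first-dose start is a lesser matter. It brings in events that home dosing could not have caused. It also admits early events that may themselves influence the investigator's judgement of suitability for home dosing (Protocol 4.3.2.1), so they could differ between groups for reasons unrelated to where doses were given.

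**What to change.** State in SAP 5.6.8 that the by-group AE overview, ISR, systemic injection reaction, hypersensitivity and medication-error tables:

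- use OH-SE. At the interim, limit this to participants who reached Week 26 by the cut-off, because OH-SE as worded keeps those who have not yet got there (at most about 192 − 180 = 12, from the Week 52 figures in SAP 5.8.1);
- count events with onset from Week 26 in both groups, as the injection-level analysis does;
- show exposure by group from Week 26 (administrations and weeks), or exposure-adjusted rates;
- carry a note that late starters and investigator selection still separate the groups.

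SE can stay for describing uptake. The cost is SAP wording only, since OH-SE and the Week 26 start are already in the plan. The downsides are that events before Week 26 appear only in the overall safety tables, and that the smaller late-starter gap and the selection remain. No analysis set removes the selection.

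### SAP 5.6.8's by-group reaction tables count events from first dose and fix no analysis set, so the ever versus never home-dosed contrast is not like for like

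*SAP*

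**What the plan says.** SAP 5.6.8 plans two comparisons of home-dosing safety.

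**Participant level.** There are two groups: "Participants who have had no home administrations by their study partner", and those with at least one such dose. By group there is an AE overview, then "Selected AE tables of ISRs, systemic injection reactions, and hypersensitivity will provide the frequency of these events by group", and a descriptive summary of medication errors. None of this sets a start date for events or names an analysis set. The section's sentence on sets, "The summaries above will be presented for the SE, OH-SE, and/or the H-SE analysis set as appropriate", comes before the grouping and refers back to the list above it.

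The general rules therefore govern:

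- SAP 5.6.2, counting: "The frequency of each AE preferred term will be defined as the number of participants experiencing at least one occurrence of the event". The summary tables take events from the day of first study drug.
- SAP 5.6.2, denominator: "Percentages will be based on the number of participants in the SE analysis set".
- SAP 5.1 refers to "analyses of home administrations by study partner that will be performed on the SE, OH-SE, or H-SE analysis sets, as appropriate". OH-SE, defined in SAP 4 as SE participants who had not stopped study drug before Week 26, is therefore allowed but not required.

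**Injection level.** "On the injection level, each single injection of study drug from Week 26 onwards" is classified by who gave it and where. ISRs, systemic injection reactions, hypersensitivity and medication errors are then expressed per administration, not per participant.

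**The concern.** The grouping is a post-baseline fact. To enter the ever group, a participant must still be on treatment at Week 26; to enter the never group, no such condition holds. Two distortions follow:

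1. **Injection count.** If SE is used, everyone who stops before Week 26 is placed in the never group with few injections and so little chance of a reaction.
2. **Attribution.** Reactions to clinic injections given before home dosing was possible are counted for the group joined later. This happens on OH-SE as well, because OH-SE removes people, not events.

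SAP 5.8.1 lists the safety of home administration among the contents of the interim CSR, which is meant to support a potential filing. A reader of that report could meet two neighbouring tables on the same question that disagree even when risk per injection is identical.

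**Working it through.** **Dose count (reproduces the protocol).** Protocol 4.3.2.1 gives 3 doses at 120 mg Q4W, 3 at 255 mg Q4W, 6 at 255 mg Q2W, then weekly doses from Week 36. To Week 103 that is 3 + 3 + 6 + 68 = 80, matching the 80 in Protocol 4.6.3. Doses before Week 26 fall on Day 1 and Weeks 4, 8, 12, 16, 20 and 24: 7 doses, all in clinic. From Week 26 there are 80 - 7 = 73.

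**Assumptions (not in the documents).**
- Equal and independent ISR risk p = 0.6% per injection in both groups. Over 80 injections this gives 1 - 0.994^80 = 38%; Protocol 5.1.1.2 reports 40.0% in one earlier open-label extension.
- Constant stopping hazard, with 10% or 20% stopped by Week 104.
- Partner home dosing taken up at Week 26 by 50%, 70% or 90% of those still on treatment, unrelated to earlier reactions.

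**Formula.** P(at least one ISR in k injections) = 1 - (1 - p)^k, averaged over stopping times.

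**One case in full: SE, 20% stopping, 70% uptake, to Week 104.**
- Stopped before Week 26: 1 - 0.80^(26/104) = 5.4%. They have 1 to 7 injections and average about 2.2% with an ISR.
- Still on treatment at Week 26: 94.6%. Their ever-ISR proportion is 35.6%, whichever group they join.
- Ever group: 35.6%.
- Never group: 0.30 × 94.6% = 28.4% of all participants, plus the 5.4% early stoppers. Ever-ISR = (28.4 × 0.356 + 5.4 × 0.022) / 33.8 = 30.2%.
- Ratio: 35.6 / 30.2 = 1.18, with no true difference.

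**Ever/never ratio on SE.**

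| Stopping by Week 104 | 50% uptake | 70% uptake | 90% uptake |
|---|---|---|---|
| 10% | 1.05 | 1.08 | 1.25 |
| 20% | 1.11 | 1.18 | 1.52 |

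At 70% uptake, p = 0.3% and p = 1.0% give the same ratios to within 0.01. On OH-SE, under these assumptions, every cell is 1.00.

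**Attribution.** The chance of at least one ISR in the first 7 injections is 1 - 0.994^7 = 4.1%. In the ever group at 20% stopping, 4.1 / 35.6 = about 12% of participants counted with an ISR had one before any home dose was possible. If follow-up were cut at Week 52 for everyone, the share would be about 26%. That is towards the upper end for the interim, since many participants will have been followed for longer.

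**Noise.** For the worked case, the approximate 95% interval around 1.18 with 192 participants is 0.76 to 1.83.

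**The case against.** The strongest reply is that the section already contains the right analysis. The injection-level table starts at Week 26, assigns each event to the way that injection was given, divides by administrations, and goes into the same interim report. With equal risk per injection it shows no difference. This stands, and it caps the weight of the point. A reader might infer that the SAP offers no exposure-based comparison of home dosing; that would be wrong.

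Second, OH-SE was evidently defined for this purpose, and the ratios above arise only if SE is chosen. This also stands. What remains is that the choice is left open, and that choosing OH-SE does not change the first-dose event window.

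Third, a reader might infer that early ISRs steer participants away from partner dosing and so make home dosing look safer. Protocol 4.3.2.1 does let the investigator or caregiver judge home dosing unsuitable at any time, but nothing in the documents gives such an effect a size. Protocol 5.1.1.2 describes ISRs in earlier studies as non-serious and mostly mild, with few or no discontinuations. Someone who gives up home dosing after one dose also stays in the ever group. In the model above, if an early ISR cut uptake from 80% to 75% (assumed), the OH-SE ratio at Week 104 would be about 0.98; a fall from 80% to 50% would be needed to reach 0.87 to 0.89. This part is speculative and carries no weight here.

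Finally, SAP 2 and 5.1 make all analyses descriptive or exploratory, so no decision rule depends on these tables.

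**Conclusion.** The point holds as a minor one. The by-group participant tables inherit a first-dose event window that credits pre-Week-26 clinic reactions to a group defined later, and they leave open a set on which early stoppers dilute the never group. With equal risk per injection, the SE contrast is about 1.05 to 1.5 at 10-20% stopping and 50-90% uptake; on OH-SE without selection it is 1.00. Stopping, uptake, risk per injection and independence between injections are all assumptions.

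A reader might infer a near-doubling, because 35% stopping with 90% uptake gives 1.99. The documents do not support using 35% as a stopping rate: SAP 3 applies it as an upper allowance for drop-out, drug discontinuation and uncertainty in the standard deviation together.

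The consequence is a descriptive table that can mislead beside one that does not. The distortion would usually lie within sampling noise.

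**What to change.** In SAP 5.6.8, state that:

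- the by-group tables of ISRs, systemic injection reactions, hypersensitivity and medication errors use OH-SE and count events from Week 26 onwards;
- each shows events per 100 injections from Week 26 beside the percentage of participants;
- the injection-level table is the main comparison of home-dosing safety.

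The rate column is needed. If first home doses were spread evenly over Weeks 26 to 52 (assumed, 70% uptake), the participant percentage on OH-SE from Week 26 would still give a ratio of 1.04 at 10% stopping and 1.09 at 20%, while the rate would be 0.60 per 100 injections in both groups.

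The cost is a filter and one column in tables already planned, using a set and a start date the SAP already has. Early stoppers leave these tables (about 5 of 192 at 10% stopping, 10 at 20%) but stay in the main AE tables. The change does not remove events between Week 26 and a later first home dose, or other selection into home dosing, and it leaves the by-group AE overview as it is.
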